16.8.4 Respiratory Referrals

Subjects with a medical history of asthma will be referred to the physician who manages their asthma when:

- ACT score ≤ 19 (an ACT score ≤ 19 conveys asthma that may not be adequately controlled).
- Unexpected worsening of asthma is observed or reported at any time during the study.
- At any study visit, subjects without a medical history of asthma will be referred to an appropriate specialist physician whenever:
 - Signs and/or symptoms suggestive of asthma are newly observed or reported.
 - Respiratory assessments (e.g., examination,) suggest a worsening in the subject's respiratory health.
- PEF value is only supplemental to the clinical evaluation of respiratory signs and symptoms suggestive of asthma (de novo or worsening in patients with history of asthma) at investigators judgement.

16.9 Adverse Events

An AE is defined as any untoward medical occurrence in a clinical study subject administered a medicinal product which does not necessarily have a causal relationship with this treatment. An AE can therefore be any unfavorable and unintended sign (including an abnormal laboratory finding), symptom, or disease temporally associated with the use of a medicinal (investigational) product, whether or not it is related to the medicinal (investigational) product. This includes an exacerbation of pre-existing conditions or events, intercurrent illnesses, drug interaction, or the significant worsening of the indication under investigation that is not recorded elsewhere in the eCRF under specific efficacy assessments.

Note(s):

- Any new sign or symptom reported by the subject that appears after accidental or intentional overdose or misuse of study drug should be reported as an AE.
- Whenever possible, a diagnosis should be reported on the AE form, instead of signs, symptoms, or abnormal laboratory values.
- Pregnancy is not to be considered an AE; however, it must be monitored and reported as described in Section 16.12.4.
- Each worsening of a chronic disease from the screening visit should be reported as a new AE.

The investigator or designee will report all AEs that occur from the time the ICF is signed until the end of the study. The sponsor/CRO should be informed if the investigator becomes

aware of any safety information that appears to be drug-related, even after the subject has completed the clinical study.

At each post enrollment visit, the investigator (or sub-investigator) will question the subject about AEs using an open nonpersuasive question to elicit reporting of AEs (for example, “Have you noticed any change in your health since the last visit?”). Directed questioning and examination will then be performed as appropriate.

Any AE occurring during the AE reporting period, whether it is related to the study drug(s) or not, will be recorded immediately in the source document and described on the Adverse Event Form (“AE Form”) along with the date of onset, severity, relationship to the study drug(s), and outcome, without omitting any requested and known information. Additional information will be requested under certain circumstances.

AEs assessed as related to the treatment or study procedure will be monitored until they have resolved or reached a stable condition. Other AEs will be monitored until the last visit if they have not resolved or reached a stable condition.

The investigator will obtain and maintain in the subject's files all pertinent medical records, information and medical judgment from colleagues who assisted in the treatment and follow-up of the subject. If necessary, the investigator will contact the subject's personal physician or hospital staff to obtain further details.

16.9.1 Assessment of Severity

Each AE will be assigned a category by the investigator as follows:

- **Mild:** An AE that is easily tolerated by the subject, causes minimal discomfort, and does not interfere with everyday activities.
- **Moderate:** An AE that is sufficiently discomforting to interfere with normal everyday activities; intervention may be needed.
- **Severe:** An AE that prevents normal everyday activities; treatment or other intervention usually needed.

16.9.2 Assessment of Causality

The investigator is to determine whether there is a reasonable causal relationship between the occurrence of the AE and exposure to the study drug (i.e., nemolizumab or placebo) and/or study procedure (e.g., injection, topical background therapy, blood sample collection). Medical judgment should be used to determine the relationship, considering all relevant factors including the pattern of the reaction, temporal relationships, relevant medical history, and confounding factors such as co-medication or concurrent diseases.

The expression “reasonable causal relationship” is meant to convey in general that there are facts or arguments to suggest a causal relationship (ICH E2A, Section IIIA 1).

The relationship assessment for an AE is to be completed using the following definitions as a guideline for all AEs occurring during this clinical study:

- **Reasonable Possibility:** According to the reporting investigator, there is a reasonable possibility (i.e., suggestive evidence or arguments) that there is a causal relationship irrespective of the dose administered:
 - Between the study drug and the AE, and/or
 - Between the clinical study protocol procedure (e.g., injection, topical background therapy, blood sample collection) and the AE.
- **No Reasonable Possibility:** No suggestive evidence or arguments can be identified regarding a causal relationship between the study drug or the clinical study protocol procedure and the AE.

16.9.3 Action Taken

The investigator will describe the action taken with the study drug for the AE in the appropriate section of the eCRF.

16.9.4 Follow-up of Adverse Event

All investigators should follow-up with subjects with AEs until the event is resolved or until, in the opinion of the investigator, the event is stabilized or determined to be chronic. Details of AE resolution must be documented in the eCRF.

Subjects should be followed up for 12 weeks (\pm 5 days) after receiving the last dose of study drug, and any AEs that occur during this time should be reported according to the procedures outlined above.

16.9.5 Documenting and Reporting of Adverse Events

AEs should be reported and documented in accordance with the procedures outlined below. All AEs occurring during the study must be documented on the relevant eCRF pages. The following data should be documented for each AE:

- Description of the symptom event
- Classification of “serious” or “not serious”
- Severity
- Date of first occurrence and date of resolution (if applicable)
- Action taken with study drug
- Other action taken (e.g., concomitant medication, other intervention)
- Causal relationship

- Outcome of event (unknown, recovered, not yet recovered, recovered with sequelae, death [with date and cause reported])

16.10 Adverse Events of Special Interest

An AESI is a noteworthy treatment-emergent event for the study drug that should be monitored closely and reported promptly. See Section [16.12.1](#) for reporting procedure. An AESI can be either serious or non-serious.

Based on the potential risks of nemolizumab and the risks associated with biologics (and their biosimilar equivalents) in general (i.e., class effects), the following AEs will be considered AESIs:

- IRRs
 - Anaphylactic reactions
 - Acute allergic reactions requiring treatment
 - Severe injection site reactions with a duration greater than 24 hours
- Newly diagnosed asthma or worsening of asthma
 - More specifically, subjects with a medical history of asthma will be referred to the physician who manages their asthma when:
 - ACT score ≤ 19 : An ACT score ≤ 19 conveys asthma that may not be adequately controlled. An AESI is reported based on the investigator's clinical judgment, including consideration of the managing physician's report.
 - Unexpected worsening of asthma is observed or reported. An AESI is reported based on the investigator's clinical judgment.
 - Subjects without a medical history of asthma will be referred to an appropriate respiratory physician/specialist when:
 - Signs and/or symptoms suggestive of asthma have been observed or reported. An AESI is reported based on the investigator's clinical judgment of the specialist's report.
 - Respiratory assessments (e.g., examination) suggest a worsening in the subject's respiratory health. An AESI is reported based on the investigator's clinical judgment of the specialist's report.
 - PEF value is only supplemental to the clinical evaluation of respiratory signs and symptoms suggestive of asthma (de novo or worsening in patients with history of asthma) at investigators judgement.
- Infections

- Any severe infection or any infection requiring treatment with parenteral antibiotics or oral antibiotics/antivirals/antifungals for > 2 weeks
- Confirmed or suspected COVID-19
- Peripheral edema: limbs, bilateral, if assessed by the investigator as having a reasonable possibility for a relationship to study drug. Peripheral edema is only to be reported as an AESI if assessed by the investigator as having a reasonable possibility for a relationship to study drug.
- Facial edema
- Elevated ALT or AST ($> 3 \times \text{ULN}$) in combination with elevated bilirubin ($> 2 \times \text{ULN}$). These abnormal lab findings may indicate potential severe liver injury (possible Hy's Law) and should be reported as an SAE (see Section 16.12.2, procedure for reporting a serious adverse event).

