12.1.1 Incidence of Adverse Events

An overall summary table with count and percentage of subjects with TEAEs and count of events will include:

- TEAEs
- TEAEs by greatest severity
- TEAEs by closest relationship to study drug
- TEAEs by closest relationship to study procedures

- TEAEs leading to treatment discontinuation
- TEAEs leading to study discontinuation
- TEAEs of special interest
- TEAEs of special interest by greatest severity
- TEAEs due to COVID-19
- Asthma-related TEAEs adjudicated by IAC
- Asthma-related TEAEs adjudicated by IAC by greatest severity
- Asthma-related TEAEs adjudicated by IAC by closest relationship to study drug
- Serious TEAEs (both fatal and non-fatal)
- Non-fatal serious TEAEs
- TEAEs leading to death
- Serious TEAEs by closest relationship to study drug
- Serious TEAEs by closest relationship to study procedures
- Serious TEAEs leading to treatment discontinuation
- Serious TEAEs leading to study discontinuation

The incidence of AEs will be summarized in tables with count and percentage of subjects with AEs and count of events by system organ class (SOC) and preferred term (PT). Unless otherwise specified, at each level of SOC or preferred term, a subject with multiple events will only be counted once per SOC or preferred term. AEs will be displayed by treatment for the Safety Set.

The following categories of AE will be summarized by SOC and PT:

- TEAEs
- TEAEs by greatest severity
- TEAEs related to study drug
- TEAEs related to study procedures
- TEAEs leading to treatment discontinuation
- TEAEs leading to study discontinuation
- TEAEs of special interest
- TEAEs of special interest by greatest severity
- TEAEs due to COVID-19
- Asthma-related TEAEs adjudicated by IAC

- Asthma-related TEAEs related to study drug adjudicated by IAC
- Asthma-related TEAEs reported by Investigator with adjudication outcome by IAC
- Asthma-related TEAEs related to study drug reported by Investigator with adjudication outcome by IAC
- Asthma-related TEAEs adjudicated by IAC by greatest severity
- Asthma-related TEAEs related to study drug adjudicated by IAC by greatest severity
- Serious TEAEs (both fatal and non-fatal)
- Non-fatal serious TEAEs
- TEAEs leading to death
- Serious TEAEs related to study drug
- Serious TEAEs related to study procedures
- Serious TEAEs leading to treatment discontinuation
- Serious TEAEs leading to study discontinuation

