Table 14.3.1.2	Summary of Treatment-Emergent Adverse Events by System Organ Class and Preferred Term	Safety Set
Table 14.3.1.3	Summary of Treatment-Emergent Adverse Events by Greatest Severity, System Organ Class and Preferred Term	Safety Set
Table 14.3.1.4	Summary of Treatment-Emergent Adverse Events Related to Study Drug by System Organ Class and Preferred Term	Safety Set
Table 14.3.1.5	Summary of Treatment-Emergent Adverse Events Related to Study Procedures by System Organ Class and Preferred Term	Safety Set
Table 14.3.1.6	Summary of Treatment-Emergent Adverse Events Leading to Treatment Discontinuation by System Organ Class and Preferred Term	Safety Set
Table 14.3.1.7	Summary of Treatment-Emergent Adverse Events Leading to Study Discontinuation by System Organ Class and Preferred Term	Safety Set
Table 14.3.1.8	Summary of Treatment-Emergent Adverse Events of Special Interest by System Organ Class and Preferred Term	Safety Set
Table 14.3.1.9	Summary of Treatment-Emergent Adverse Events of Special Interest by Greatest Severity, by System Organ Class and Preferred Term	Safety Set
Table 14.3.1.10	Summary of Treatment-Emergent Adverse Events due to COVID-19 by System Organ Class and Preferred Term	Safety Set
Table 14.3.1.11	Summary of Asthma-Related Treatment-Emergent Adverse Events Adjudicated by IAC by System Organ Class and Preferred Term	Safety Set
Table 14.3.1.12	Summary of Asthma-Related Treatment-Emergent Adverse Events Related to Study Drug Adjudicated by IAC by System Organ Class and Preferred Term	Safety Set
Table 14.3.1.13	Summary of Asthma-Related Treatment-Emergent Adverse Events Reported by Investigator with Adjudication Outcome by IAC by System Organ Class and Preferred Term	Safety Set
Table 14.3.1.14	Summary of Asthma-Related Treatment-Emergent Adverse Events Related to Study Drug Reported by Investigator with Adjudication Outcome by IAC by System Organ Class and Preferred Term	Safety Set
Table 14.3.1.15	Summary of Asthma-Related Treatment-Emergent Adverse Events Adjudicated by IAC, by Greatest Severity, System Organ Class and Preferred Term	Safety Set
Table 14.3.1.16	Summary of Asthma-Related Treatment-Emergent Adverse Events Related to Study Drug Adjudicated by IAC, by Greatest Severity, System Organ Class and Preferred Term	Safety Set

TLF	Title	Analysis Set
Table 14.3.1.17	Summary of Serious Treatment-Emergent Adverse Events by System Organ Class and Preferred Term	Safety Set

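### AESIs are defined by clinical category but tabulated only pooled and by SOC/PT, so injection-related reactions and non-COVID AESI infections get no once-per-subject count by arm

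*Protocol*

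**What the plan says.** Protocol 16.10 lists six categories:

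- Injection-related reactions, in three parts: anaphylaxis, acute allergic reactions that need treatment, and "Severe injection site reactions with a duration greater than 24 hours".
- "Newly diagnosed asthma or worsening of asthma".
- Infections, in two parts: "Any severe infection or any infection requiring treatment with parenteral antibiotics or oral antibiotics/antivirals/antifungals for > 2 weeks", and "Confirmed or suspected COVID-19" with no severity threshold.
- Limb edema, which counts only when a link with the drug is thought possible: "Peripheral edema is only to be reported as an AESI if assessed by the investigator as having a reasonable possibility for a relationship".
- Facial edema.
- Raised ALT or AST together with raised bilirubin, of which the protocol says "These abnormal lab findings may indicate potential severe liver injury (possible Hy's Law) and should be reported as an SAE".

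Protocol 19.4.2 promises a summary table of AESIs but does not fix its layout. SAP 12.1.1 puts AESIs in the overall table (14.3.1.1) as one line and again by greatest severity. It then introduces the detailed tables with "The following categories of AE will be summarized by SOC and PT". For AESIs these are Table 14.3.1.8, "Summary of Treatment-Emergent Adverse Events of Special Interest by System Organ Class and Preferred Term", and Table 14.3.1.9, which adds greatest severity. Unless otherwise specified, a subject is counted once per SOC or preferred term. Listing 14.3.2.5 gives AESIs by subject.

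**The concern.** A MedDRA term names a diagnosis. It does not say whether an infection was treated parenterally, whether oral treatment passed two weeks, or whether an injection site reaction lasted more than 24 hours. A layout by SOC and preferred term therefore need not reproduce the protocol's categories. If a category spreads over several terms or classes, a subject with two events can appear in two rows, and adding rows does not give the number of subjects affected.

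This matters because protocol 8.4 names injection-related reactions, asthma and infections as the potential risks of the drug. Protocol 19.6 and SAP 15 make the choice between two doses a risk-benefit judgement at the final analysis. For that judgement a reader wants the number of subjects per arm in each category. A grouping of terms chosen after unblinding is open to the charge that it was chosen to suit the data.

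**Working it through.** The plan states no figure on this point, so the main check sets definitions against outputs. SAP Appendix F lists Tables 14.3.1.1 to 14.3.1.23 without a break in numbering, so a redacted table does not explain the gap.

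**Step 1. Category against planned display**

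| Protocol 16.10 category | Nearest planned display | Once-per-subject count of the category? |
|---|---|---|
| Injection-related reactions | Term rows in 14.3.1.8 and 14.3.1.9 | No, if the three parts code to more than one term or class |
| Asthma | 14.3.1.11 to 14.3.1.16 | Own tables |
| Infections, both parts together | Infections SOC row in 14.3.1.8 | Approximately, if all such events code to that SOC |
| Severe infections | Infections SOC by severity in 14.3.1.3 and 14.3.1.9 | Yes by SOC, but severe COVID-19 is included |
| Non-COVID infections meeting the AESI criterion | None; a moderate infection that qualified through its treatment has no marker | No |
| COVID-19 | 14.3.1.10 and a line in 14.3.1.1 | Own table |
| Limb edema judged related; facial edema | Term rows in 14.3.1.8; related events also in 14.3.1.4 | Yes, if each codes to one term |
| ALT/AST with bilirubin | eDISH plot (Figure 14.3.4.2.15); potentially clinically significant values (Table 14.3.4.2.4) | Own displays, not an AESI count |

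**Step 2. Can COVID-19 be subtracted?** Let A be subjects with any non-COVID AESI and C subjects with COVID-19. Then

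N(A) = N(any AESI) − N(C) + N(A and C).

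The planned tables do not give the last term. Subtraction is exact when no subject has both and otherwise too low by the overlap. Assume a 10% non-COVID AESI risk in an arm of 84 (8.4 subjects expected) and independence. The expected overlap is 84 × 0.10 × c, where c is the COVID-19 rate:

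- c = 5%: 0.42 subjects
- c = 10%: 0.84 subjects
- c = 20%: 1.68 subjects

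The relative shortfall equals c. The same identity holds for non-COVID infections within the infections SOC row.

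**Step 3. Dilution of the any-AESI line.** With non-COVID AESI risk p and COVID-19 rate c, equal in both arms and independent, the line shows q = 1 − (1 − p)(1 − c). The documents give neither p nor c, so all inputs are assumed. For example, with c = 10%: 1 − 0.98 × 0.90 = 11.8%, and 1 − 0.90 × 0.90 = 19.0%.

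| c | p = 2% and 10% (ratio 5.0) | p = 4% and 12% (ratio 3.0) |
|---|---|---|
| 5% | 6.9% and 14.5%, ratio 2.1 | 8.8% and 16.4%, ratio 1.9 |
| 10% | 11.8% and 19.0%, ratio 1.6 | 13.6% and 20.8%, ratio 1.5 |
| 20% | 21.6% and 28.0%, ratio 1.3 | 23.2% and 29.6%, ratio 1.3 |

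The difference shrinks only by the factor (1 − c): 8.0 points become 7.6, 7.2 and 6.4. The ratio suffers far more.

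**The case against.** The strongest reply is that this is table layout. The protocol asks for an AESI summary without specifying categories, and the SAP supplies one overall, by severity, by SOC and term, and as a listing. The row layout belongs to the table shells, which SAP 17 keeps in a separate document. No test or estimate depends on it. All of that is fair: there is no contradiction between the documents, and the shells may already group rows. The titles in Appendix F, however, state a SOC/PT layout, and the SAP text has no rule for counting a subject once per category.

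Some stronger readings are tempting, but the documents do not support them:

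- *That severe infection and edema have no per-arm figures.* Tables 14.3.1.3 and 14.3.1.9 show severe events in the infections SOC by arm. Limb edema counts as an AESI only if judged possibly related, so its rows in Table 14.3.1.8 already describe drug-related edema.
- *That the missing counts are lost.* Listings 14.3.2.4 and 14.3.2.5 give severe events and AESIs by subject, and SAP 4 sorts listings by treatment. With about 84 subjects per arm a hand count is feasible.
- *That the layout would hide a known dose trend in edema.* Protocol 8.4 reports the slight trend in study CIM003JG. The figures it prints, 3.6%, 3.6%, 7% and 3.5% for placebo, 10, 30 and 90 mg, come from SPR.114322. There the highest dose is level with placebo, so they show no dose trend.

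**Conclusion.** The concern holds in limited form. No planned table gives a per-arm count, each subject once, of injection-related reactions or of non-COVID infections meeting the AESI criterion. The any-AESI line mixes every COVID-19 case with the other categories. For injection-related reactions this assumes that the three parts code to more than one term or class. For treatment-defined infections no coding assumption is needed, because neither term nor severity carries the criterion.

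The size is modest. Under the assumed rates above, COVID-19 in 5% to 20% of subjects cuts a ratio of 5.0 to between 2.1 and 1.3, and the error from subtracting COVID-19 is under two subjects per arm. Using Table 14.3.1.10 for the subtraction further assumes that its events match the COVID-19 AESIs, which the SAP does not say. Primary and key secondary analyses are unaffected. The value of a change lies in fixing the risk groupings before the data that inform dose selection are unblinded.

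**What to change.** Before unblinding, and so before the shells are final:

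1. In SAP 12.1.1, flag each AESI record with its protocol 16.10 category and sub-category, with COVID-19 as its own sub-category whatever its severity. State that a subject is counted once per category and once per sub-category.
2. In Tables 14.3.1.1, 14.3.1.8 and 14.3.1.9, add rows by category and sub-category. In the last two, show preferred terms within category.
3. Show COVID-19 separately from other infections, and add an any-AESI line that excludes COVID-19.

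The cost is one derived flag and somewhat longer tables. The AESI report (protocol 16.12.1), event severity (16.9.5) and concomitant therapies (12.5) are already collected, so no new data collection should be needed. Assigning the flag takes a short blinded medical review where a record could fit more than one category.

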16.11 Serious Adverse Events

An SAE is any untoward medical occurrence or effect that, at any dose:

- Results in death.
- Is life-threatening (an AE is life-threatening if the subject was at immediate risk of death from the event as it occurred, i.e., it does not include a reaction that might have caused death if it had occurred in a more serious form).
- Requires or prolongs inpatient hospitalization (Complications occurring during hospitalization are AEs and SAEs if they cause prolongation of the current hospitalization. Inpatient hospitalization is considered to have occurred if the subject has had to stay for a night at the hospital. The criterion for prolongation of hospitalization is also defined as an extra night at the hospital. Hospitalization may not constitute sufficient grounds to be considered as an SAE if it is solely for the purpose of diagnostic tests [even if related to an AE], elective hospitalization for an intervention that was already planned before subject enrollment in the clinical study, admission to a day care facility, social admission [e.g., if the subject has no place to sleep], or administrative admission [e.g., for a yearly examination]. The details of such hospitalizations must be recorded on the medical history or physical examination eCRF).
- Results in persistent or significant disability/incapacity (An AE is incapacitating or disabling if it results in a substantial and/or permanent disruption of the subject's ability to carry out normal life functions).
- Results in a congenital anomaly/birth defect.
- An important medical event that may not result in death, be life-threatening, or require hospitalization, may be considered an SAE when, based upon appropriate medical judgment, the event may jeopardize the safety of the subject, and may require medical

or surgical intervention to prevent 1 of the outcomes listed above in this definition. Examples of such events are intensive treatment in an emergency room or at home for allergic bronchospasm, blood dyscrasias, or convulsions that do not result in hospitalization.

